5.0 Recruitment

Recruitment for the study will be done using various recruitment platforms and methods described below:

Posting and distributing IRB approved flyers around the community:

- IRB approved flyers will be posted in and around the community. The flyers will be distributed using methods including but not limited to:
 - Approved flyers will be posted on billboards.
 - Posting and handing flyers to the public in locations such as Malls, Airports, parks, recreation centers, restaurants etc.
- Posting IRB approved Ads on Shuttles and buses – Emory University buses/shuttles, Georgia Tech shuttles/buses, MARTA buses and bus stops
- The Hope Clinic team will take part in community events throughout Atlanta where study staff will talk to attendees about research studies being done at the Hope Clinic, including this study.

The study team will ensure that in locations where required, permission from relevant authorities will be sought before distributing or posting the flyers.

Social media and paid advertising:

- Posting ads on different social media platforms such as Facebook, Instagram, Twitter, Snapchat, TikTok etc. and dating apps containing a link to the Hope Clinic Volunteer Form.
- The Emory Hope Clinic website (A short description of the study will be put on the Hope Clinic website using the same language as the ads).
- IRB approved Ad banners may also be placed on streaming platforms including but not limited to Netflix, Hulu, Disney+ etc.
- We may also partner with cable companies such as AT&T, Xfinity etc. to post paid ads. The ads may be posted in the form of texts, email or banner on cable TV.

Recruiting via email:

- Email blasts of IRB approved email language will be sent out on various listservs e.g., Emory Vaccine Dinner Club, Emory Vaccine Center, CDC etc.
- Email blasts to student listservs including Emory University, Georgia State University, Georgia Tech and UGA. The study team will seek approval from the respective universities registrars and verify the method in which the email blast will be sent out (listservs or individual email).

Registries

- We may also use registries as a recruitment platform for this protocol. Various volunteer registries may be utilized. After potential candidates have been identified from the registry, they may be contacted by their indicated method of contact (email, mailing address or phone/texting) and invited to be screened under this protocol.

Contacting past and present study subjects

- Current and past Hope Clinic subjects (i.e. who have agreed to be contacted in past informed consent forms) may be contacted by calling and emailing. Potential new subjects who will self-refer from recruitment advertisements will be included. All recruitment materials will be IRB approved prior to use. IRB approved advertisements may be placed in local media platforms.

Verbal/written consent is first obtained and then subjects will be interviewed to assess if they meet the inclusion and exclusion criteria. They will be enrolled and undergo the screening procedures indicated unless it is discovered that they are not eligible to continue.

5 STUDY PROCEDURES/EVALUATIONS

5.1 Study Procedures

Medical history will be obtained by interview of study subjects on Day 1 (Visit 1) prior to the study vaccination. Subjects will be asked about a known history of significant medical disorders, cancer, immunodeficiency, allergies, psychiatric illness, substance use, and autoimmune diseases.

Medications history will include a review of all current medications and any medications taken in the last 30 days before study vaccination. Medications included in this history will include prescription medication, over-the-counter medication, vitamins, supplements, and prohibited treatments listed in the above Inclusion/Exclusion Criteria section, such as antibiotics within the last 14 days and vaccines.

On Day 1 (Visit 1) and before the study vaccination, a targeted physical examination may be performed by the investigator, who is licensed to make medical diagnoses. At visits 2-7, a targeted physical examination may be performed based on interim health history.

Vital signs (oral temperature, pulse rate, and blood pressure) will be measured at all study visits.

Height and weight will be measured on Day 1 (Visit 1) before study vaccination

Subjects will be observed in the clinic for at least 20 minutes after study vaccination on Day 1 (Visit 1).

5.1.1 Laboratory Evaluations/Assays

Urine pregnancy tests will be performed by the site laboratory on the same day as and prior to study vaccination (Day 1). Results must be negative and known prior to study vaccination.

5.1.2 Special Assays or Procedures

The immunologic assays will be performed at [name] on the Emory University main campus.

5.1.3 Specimen Collection, Preparation, Handling and Analyses

Blood will be collected at each of the seven study visits as per the Study Schedule in Appendix A.

6 STUDY SCHEDULE

6.1 Screening and Enrollment/Baseline Visit

6.1.1 Screening Visit Day 00 (As needed) (Day -45 to -7 days)

Study subjects will be given a description of the study and have an opportunity to have their questions and concerns addressed by the study principal investigator or designee.

Subjects will be given the informed consent form to read and discuss with study staff, and if they wish to enroll will sign the document before any study vaccination, procedures, or lab draws are performed.

A medical history and targeted physical exam, if necessary, as outlined in the Study Procedures section will be conducted in order to assess for compliance with study inclusion and exclusion criteria.

A list of any medications taken by subjects in the past 30 days and those to be taken for 28 days after vaccinations will be documented on the appropriate study form.

A urine pregnancy test will be conducted for female subjects, and a negative result will be required and be documented on the appropriate study form prior to any study interventions.

Vital signs, including pulse rate, blood pressure, oral temperature, and height and weight will be measured and documented on the appropriate study form.

Group 1 and Group 2 subjects: a procedure for small intestinal biopsies using esophagogastroduodenoscopy will be performed by a gastrointestinal specialist at Emory GI suite. Visit will take 4 hours.

6.1.2 Visit 0a (screening+7) for groups 1 and 2

Groups 1 and 2: a follow-up phone call is made 7 days post procedure to assess for any adverse events from the EGD procedure.

6.1.3 Enrollment Day 01

Study subjects will be given a description of the study and have an opportunity to have their questions and concerns addressed by the study principal investigator or designee.

Subjects will be given the informed consent form to read and discuss with study staff (if no screening visit has been done), and if they wish to enroll will sign the document before any study vaccination, procedures, or lab draws are performed.

A medical history and targeted physical exam, if necessary, as outlined in the Study Procedures section will be conducted in order to assess for compliance with study inclusion and exclusion criteria.

A list of any medications taken by subjects in the past 30 days and those to be taken for 28 days after vaccinations will be documented on the appropriate study form.

A urine pregnancy test will be conducted for female subjects, and a negative result will be required and be documented on the appropriate study form prior to any study interventions.

Vital signs, including pulse rate, blood pressure, oral temperature, and height and weight will be measured and documented on the appropriate study form.

Blood will be collected for baseline study labs as outlined in the Study Procedures section.

A single dose of the FDA-approved oral live cholera vaccine (Vaxchora) will be administered. Eating and drinking should be avoided for one hour before and after vaccine administration. Subjects will be asked to remain at the clinic for 20 minutes to monitor for any reactions or adverse events. Any reactions or adverse events will be documented on the appropriate study form. Subject will be instructed to use adequate hand hygiene to avoid fecal-oral transmission of the vaccine to others.

Subjects will be informed to contact the study clinic should they experience any concerning reactions to the vaccine, and they will be asked to visit the clinic for evaluation should the principal investigator or designee deem the reaction in need of evaluation.

6.2 Follow-up and Final Visits

6.2.1 Visit 02 Day 08 Visit 03 Day 11, Visit 04 Day 15

Interim medical history and targeted physical exam, if necessary, will be conducted.

Medications taken during the interim from the previous visit and any adverse or serious adverse events will be documented on the appropriate study form.

Vital signs, including pulse rate, blood pressure, and oral temperature will be measured and documented on the appropriate study form-

Blood will be collected for immunogenicity analysis.

A review of the memory aid will be done at Visit 02.

Certain follow up visits (D11 and D15) will not be required by PI discretion.

6.2.2 Visit 05 Day 29

Interim medical history and targeted physical exam, if necessary, will be conducted.

Medications taken during the interim from the previous visit and any adverse or serious adverse events will be documented on the appropriate study form.

Vital signs, including pulse rate, blood pressure, and oral temperature will be measured and documented on the appropriate study form.

Blood will be collected for immunogenicity analysis.

Group 1 (n=15): a small intestinal biopsy using esophagogastroduodenoscopy will be performed by a gastrointestinal specialist at Emory GI suite. Visit will take 4 hours. The window for this visit is – 7 days/ + 14 days

6.2.3 Visit 06 Day 90

Interim medical history and targeted physical exam, if necessary, will be conducted.

Any serious adverse event will be documented on the appropriate study form.

Vital signs, including pulse rate, blood pressure, and oral temperature will be measured and documented on the appropriate study form-

Blood will be collected for immunogenicity analysis

Group 2 (n=5): a small intestinal biopsy using esophagogastroduodenoscopy will be performed by a gastrointestinal specialist at Emory GI suite. Visit will take 4 hours. The window for this visit is + 14 days. Visit 05a (EGD +7 days) and Visit 06a (EGD day+7 days)

Group 1 and 2: a follow-up phone call is to be made 7 days post-procedure to assess for any adverse events from the procedure. Visit 07 Day 365

Interim medical history and targeted physical exam, if necessary, will be conducted.

Any serious adverse event will be documented on the appropriate study form.

Vital signs, including pulse rate, blood pressure, and oral temperature will be measured and documented on the appropriate study form.

Blood will be collected for immunogenicity analysis

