2.2 Study Outcome Measures

Primary:

- Level of antibody titers at day 1 (pre-vaccination) and day 29 in serum.

Secondary:

- Levels of plasmablasts at days 1, 8 and 29
- Levels of activated B cells at days 1, 8 and 29
- Levels of memory B cells at days 1 and 29 .
- Correlation between antibody titers and the level of plasmablasts, activated B cells, and memory B cells.
- Production and characterization of monoclonal antibodies at day 8 against *V. cholerae* in a subset of subjects.
- Solicited and unsolicited adverse events in healthy subjects receiving cholera vaccine at day 8 and day 29 respectively.

- Serious adverse events in healthy subjects receiving cholera vaccine for the duration of the study

Exploratory:

- Levels of plasmacells, activated B cells and T cells in small intestinal biopsy samples at day 29 (n=15) or day 90 (n=5).
- Correlation between systemic and mucosal immune responses.
- Production and characterization of monoclonal antibodies against *V. cholerae* from a protected mucosal site.
- Levels of antibody titers at days 90 and 365.
- Levels of plasmablasts at days 11 and 15 in a subset of subjects.
- Levels of activated B cells at days 11 and 15 in a subset of subjects.
- Levels of T cells at days 1 and 29 in a subset of subjects.

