6.3 Early Termination Visit (if needed)

The following will be performed at any early termination visit, if necessary, for subjects who withdraw or who are withdrawn from the study:

Interim medical history and targeted physical exam, if necessary, will be conducted.

A review of the memory aid will be conducted (if visit occurs within 7 days of vaccination).

Medications taken during the interim from the previous visit will be documented on the appropriate study form (if prior to D29).

Vital signs, including pulse rate, blood pressure, and oral temperature will be measured and documented on the appropriate study form.

Any adverse (prior to D29) or serious adverse events will be documented on the appropriate study form.

Blood will be collected for immunogenicity analysis.

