Adverse events	X	X	X	X	X	X	X				
Serious adverse events	X	X	X	X	X	X	X	X	X	X	X

#Prior to study procedures

*Prior to study vaccination.

+Not required if done at the screening visit

%All current medications and medications taken within 30 days prior to day 1 of the study.

&Vital signs assessed on Day 1 (Visit 1) before the study vaccination will be considered as baseline.

\$Subjects must not eat or drink anything hot or cold, or smoke within 10 minutes prior to taking oral temperature.

() Targeted physical examination if indicated based on review of complete or interim medical history.

@Must be performed on all female subjects of childbearing potential within 24 hours prior to each study vaccination and results must be negative and known prior to each study vaccination.

*Complete medical history by interview of subjects to be obtained on Day 0 (Visit 01) prior to the first study vaccination and interim medical history by interview of subjects to be obtained at follow-up visits after study vaccination.

!Only for participants agreeing to EGD i.e. Group 1 and 2

= Group 1 (n=25) will undergo small intestinal biopsy on D29 and Group 2 (n=5) subjects will undergo small intestinal biopsy at D90.

^Follow-up phone call post small intestinal biopsies via EGD.

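### Calls V05a and V06a are meant to find any adverse event from the endoscopy, but the schedule provides no recording of non-serious events at them, or at V06 for Group 2

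*Combined protocol and SAP*

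**What the plan says.** The text on Visits 05a and 06a (Section 6.2.4 in the table of contents) gives the purpose of the calls in Groups 1 and 2: "a follow-up phone call is to be made 7 days post-procedure to assess for any adverse events from the procedure". It does not restrict the calls to serious events.

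The recording rules elsewhere are narrower:

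- Appendix A, adverse event row: "Adverse events X X X X X X X". These seven marks fill the first seven of eleven columns, Screen to V05. The last four (V05a, V06, V06a, V07) are blank.
- Appendix A, serious adverse event row: "Serious adverse events X X X X X X X X X X X". All eleven columns are marked.
- Section 6.2.2 (V05, Day 29) covers both kinds of event: "Medications taken during the interim from the previous visit and any adverse or serious adverse events will be documented on the appropriate study form".
- Section 6.2.3 (V06, Day 90) and the text for V07 cover serious events only: "Any serious adverse event will be documented on the appropriate study form".
- Section 6.3 (early termination): "Any adverse (prior to D29) or serious adverse events will be documented on the appropriate study form".
- Section 2.2, the secondary safety outcome: "Solicited and unsolicited adverse events in healthy subjects receiving cholera vaccine at day 8 and day 29 respectively". It is not limited by cause.

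Section 6.1.2 sets up call V0a, 7 days after the screening EGD, for the same purpose as V05a and V06a. Appendix A marks V0a for adverse events.

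**The concern.** The same procedure and the same call have two recording rules, depending on whether the EGD comes before or after vaccination, and no reason is given. A site that follows the schedule would ask about any procedure event at V05a and V06a but would have a scheduled place to record only the serious ones.

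These are research biopsies in healthy volunteers. Section 1.3.1 expects complication rates below the published ones because the cohort is healthy. Without non-serious data from the post-vaccination EGDs, half of the procedures contribute little to checking that expectation. Events not entered at the call are hard to recover later.

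A related gap concerns attribution. The Group 1 EGD may be done from Day 22, V05 records all adverse events, and no rule in the documents separates procedure events from vaccine events. Section 1.3.1 lists hypotension, vasovagal episodes and arrhythmias among sedation events, and Appendix B grades hypotension and heart-rate changes, so an entry on the form would not by itself show its source.

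**Working it through.** The plan states no figure to reproduce on this point. The check sets the text beside the schedule and then works out dates and counts.

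**Text against schedule**

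| Contact | Link to EGD | Scope of events in the text | AE row | SAE row |
|---|---|---|---|---|
| V0a | call after screening EGD | any event from the procedure | marked | marked |
| V05 | Group 1 EGD visit | adverse and serious | marked | marked |
| V05a | call after Group 1 EGD | any event from the procedure | blank | marked |
| V06 | Group 2 EGD visit | serious only | blank | marked |
| V06a | call after Group 2 EGD | any event from the procedure | blank | marked |

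Text and schedule agree at V0a and V05. At V05a and V06a they conflict. At V06 they agree with each other, but the result is that the Group 2 EGD visit has no scheduled place for a non-serious event on the day of the procedure. The concomitant medication row also stops at V05, so the stop there is consistent across rows and does not look like a table lost in extraction.

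**Dates of the calls** (call day = EGD day + 7; windows from Sections 3 and 6.2)

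- Group 1: EGD on Day 29 − 7 = 22 to Day 29 + 14 = 43, so V05a falls on Day 29 to Day 50 (Day 36 at the nominal date).
- Group 2: EGD on Day 90 to Day 90 + 14 = 104, so V06a falls on Day 97 to Day 111. Under the V06 window in Appendix A (−4/+7, Day 86 to 97) it falls on Day 93 to Day 104.

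Every V06a call is well past Day 29. A V05a call falls on Day 29 only if the EGD is done on the first permitted day; otherwise it is later.

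**Procedures affected**

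- Sections 3, 4.1 and 7 give 30 EGD subjects, and Appendix A gives 25 + 5 = 30. There are 30 × 2 = 60 EGDs, of which 30 are post-vaccination.
- Sections 2.2 and 6.2 give 15 + 5 = 20, hence 20 post-vaccination EGDs of 40.

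On either count, the call after every post-vaccination EGD is affected.

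**Overlap with the Day 29 outcome in Group 1** (post-procedure days up to Day 29 = max(0, 29 − EGD day))

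- EGD on Day 22: 29 − 22 = 7 days.
- EGD on Day 29: 0 days.
- EGD on Day 43: 0 days.

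A procedure event can therefore be recorded by V05 only if it occurs on the procedure day before the V05 review, or if the EGD is done early in the window and the review follows it. Solicited events (Day 8) precede the earliest post-vaccination EGD and are not touched.

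**Scale.** Section 1.3.1 gives overall complication rates of 0.13% to 0.15% and cardiopulmonary event rates of 2 to 5.4 per 1000. The chance of at least one event in n procedures is 1 − (1 − p)^n:

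| p | n = 20 | n = 30 |
|---|---|---|
| 0.0013 | 2.6% | 3.8% |
| 0.0015 | 3.0% | 4.4% |
| 0.002 | 3.9% | 5.8% |
| 0.0054 | 10.3% | 15.0% |

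Section 1.3.1 also gives a far lower rate, 0.0002%, for diagnostic endoscopy without therapeutic maneuvers. None of these is a rate of minor, non-serious events. Some of the events counted in them would be serious and would be caught by the serious event row. They give context but do not size the gap.

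**The case against.** The strongest reply is that the call text itself tells staff to assess any procedure event, that Appendix A has a row for the call marked at V05a and V06a, and that medical history is marked there too. A careful site might well write the event down. The serious-only wording in Section 6.2.3 governs the V06 clinic visit and not the V06a call, and Section 6.3 applies only to early termination. Safety is secondary, the planned statistics are descriptive, no listed outcome measures EGD safety, and serious events are collected at every contact. The stop at V05 may simply be the vaccine safety window.

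Much of this stands. A reader might infer that non-serious events cannot be recorded at these calls. The documents do not support that; they show that no such recording is scheduled. The reply also limits the consequence, since no stated endpoint is altered by events after Day 29. It does not remove the contradiction. V0a comes before the vaccination visit, so its adverse event mark cannot serve a vaccine safety window. The row is evidently meant to cover procedure events, and it does so for one of the two EGDs.

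A reader might also infer that Group 1 procedure events are counted as vaccine events and inflate the vaccine adverse event rate. No section says so. The Group 1 EGD is listed as part of V05, nothing shows that it precedes the V05 adverse event review, and an EGD on Day 29 or later leaves no following day inside the cut-off. An outcome that counts all events whatever their cause is not wrong in itself. With no minor-event rate in the documents, any figure for such inflation would rest on assumption alone.

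**Conclusion.** The contradiction between the purpose of the V05a and V06a calls and the Appendix A adverse event row is real and must be reconciled. If the schedule is followed as written, non-serious event recording is absent at the call after all 30 post-vaccination EGDs (20 under the 15 + 5 split) and at the Group 2 EGD visit. This conclusion rests on reading the seven marks as the first seven columns, which the visit text for V05, V06 and V07 supports.

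The number of events lost is unknown. Any overlap of EGD events with the Day 29 unsolicited outcome is also of unknown size and may be nil; the point there is only that nothing in the plan would let an analyst tell the two apart. Severity is moderate: the gap affects the completeness of safety data, and the antibody endpoint is unaffected.

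**What to change.** 1. In Appendix A, mark adverse events at V05a, at V06 for Group 2, and at V06a, with a footnote limiting the new marks to EGD-related events.
2. Align Section 6.2.3 (V06) and Section 6.3 so that non-serious EGD-related events are recorded after Day 29 as well.
3. Record for each event its onset relative to the EGD and its attribution (EGD or vaccine).
4. List EGD events separately, so that any Group 1 procedure event recorded by V05 can be distinguished within the Day 29 unsolicited outcome.

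The cost is three schedule cells, matching wording in two sections, one form field and one listing. The calls are already planned, and no visit or procedure is added. The Group 1 size (15 or 25) should be settled in the same amendment, because it fixes how many procedures the listing covers.

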6.3 Early Termination Visit (if needed)

The following will be performed at any early termination visit, if necessary, for subjects who withdraw or who are withdrawn from the study:

Interim medical history and targeted physical exam, if necessary, will be conducted.

A review of the memory aid will be conducted (if visit occurs within 7 days of vaccination).

Medications taken during the interim from the previous visit will be documented on the appropriate study form (if prior to D29).

Vital signs, including pulse rate, blood pressure, and oral temperature will be measured and documented on the appropriate study form.

Any adverse (prior to D29) or serious adverse events will be documented on the appropriate study form.

Blood will be collected for immunogenicity analysis.

